### 5.3 EFFICACY

#### **ACR20/50/70**

The ACR composite score evaluates clinical improvement relative to an initial assessment for clinical trials in subjects with RA.

The ACR20 response is defined as at least 20% improvement compared to baseline for both swollen and tender joint counts (66/68 joint counts), as well as for at least 3 out of the following 5 additional parameters:

- Subject's Global Health Assessment
- Investigator's Global Health Assessment
- Subject's assessment of pain
- Health Assessment Questionnaire Disability Index (HAQ-DI)
- C-Reactive Protein (CRP)

ACR50 and ACR70 are defined in a similar fashion to ACR20 but require at least 50 and 70 percent improvement respectively. Method for handling missing data is described in the appendix 2.

#### **DAS28-CRP**

The DAS28-CRP is a composite measure of disease activity in RA. It is a continuous measure based on 28 DAS joints from the ACR, the Subject's Global Health Assessment score, and CRP, as follows:

$$\text{DAS28-CRP} = 0.56*(\text{TJC28})^{0.5} + 0.28*(\text{SJC28})^{0.5} + 0.36*\ln(\text{CRP}+1) + 0.014*\text{SGH} + 0.96$$

where TJC28 is the tender joint count of the 28 joints in the DAS, SJC28 is the swollen joint count of the 28 joints in the DAS, CRP is in mg/L, and SGH is the Subject's Global Health Assessment in 0 to 100 scale.

If the CRP is at a non-detectable level, then replace it with the minimum detectable level.

Sponsor: Amgen Inc.

Statistical Analysis Plan

Protocol No: 20130108

10-December-2018/ Version 2.0

### **DAS28-CRP Remission**

A subject will be considered to have achieved DAS28-CRP remission if the subject has a DAS28-CRP score less than 2.6.

### **Health Assessment Questionnaire – Disability Index (HAQ-DI)**

The HAQ-DI score is defined as the average of the scores from eight sub-domains (dressing / grooming, arising, eating, walking, hygiene, reach, grip, and activities). The detailed score algorithm is described in [Appendix 4](#).

### **Hybrid ACR Response**

Hybrid ACR response is a continuous score of the mean improvement in the core set measures combining the ACR20, ACR50, and ACR70 response rates.

The hybrid ACR can be calculated when all 7 components are available following the table below ([American College of Rheumatology Committee to Reevaluate Improvement Criteria, 2007](#)):

ACR Status	Mean % change in all 7 core set measures			
	<20	>=20, <50	>=50, <70	>=70
Not ACR20	Mean % change	19.99	19.99	19.99
ACR20 but not ACR50	20	Mean % change	49.99	49.99
ACR50 but not ACR70	50	50	Mean % change	69.99
ACR70	70	70	70	Mean % change

If a core set measure worsens by > 100% , the percentage change will be limited to 100%.

### **Swollen Joint Count**

The swollen joint count will be the number of joints that are assessed as swollen among the 66 joints specified in Section 17.3 of the protocol and the corresponding Joint Assessment CRF page. Method for handling missing joint assessments (including those due to artificial/fused joint or intra-articular corticosteroid injection) is defined in [Appendix 3](#).

### **Tender Joint Count**

The tender joint count will be the number of joints that are assessed as Pain/Tenderness among the 68 joints specified in Section 17.3 of the protocol and the corresponding Joint Assessment CRF page. Method for handling missing joint assessments (including those due to artificial/fused joint or intra-articular corticosteroid injection) is defined in [Appendix 3](#).

Sponsor: Amgen Inc.

Statistical Analysis Plan

Protocol No: 20130108

10-December-2018/ Version 2.0

## 5.4 SAFETY

### Adverse Event of Interest (AEOI)

An AEOI is defined as a noteworthy TEAE for a particular product or class of products that a sponsor may wish to monitor carefully. It could be serious or non-serious, and could include events that might be potential precursors or prodromes for more serious medical conditions in susceptible individuals (Council for International Organizations of Medical Sciences [CIOMS] VI, 2005). The AEOIs for this study will include:

- infusion reactions including hypersensitivity,
- cardiac disorders,
- serious infections,
- progressive multifocal leukoencephalopathy,
- hematological reactions,
- hepatitis B reaction,
- opportunistic infections
- hypogammaglobulinemia.
- severe mucocutaneous reactions,
- gastrointestinal perforation

Events of interest were identified using the latest versions of pre-specified Standardised MeDRA query (SMQ) where available. If no SMQ is available for use as a search tool for a given EOI (eg. Infusion reactions), a customized search strategy developed at Amgen or medical review will be used where SMQ is not available. [Appendix 5](#) provides the search strategy used to retrieve the events of interest. The preferred terms used in the searches are stored in a central PRA server location for analyses.

### Exposure Adjusted Incidence Rate (EAIR) for Adverse Events and Adverse Event of Interest

The exposure adjusted incidence rate is defined as the number of subjects with a particular AE divided by the total exposure-time among subjects in the respective treatment group at risk of an initial occurrence of the event. Specifically,

$$\text{Exposure Adjusted Incidence Rate} = \frac{n}{T} = \frac{n}{\sum t_i},$$

where  $n$  is the number of subjects with events,  $t_i$  is a subject's exposure time under a given unit and  $T$  is the total exposure time under a given time unit of the subjects in the group. If a subject has multiple events, the  $t_i$  is the time from the first dose date of the respective treatment to the onset of the first event. For those subjects who crossed over from one IP treatment during the 1st dose to another IP treatment during the 2nd dose, the exposure time following each of the doses will be counted in the respective treatment

Sponsor: Amgen Inc.

Statistical Analysis Plan

Protocol No: 20130108

10-December-2018/ Version 2.0

---

group. For a subject with no event, the *ti* is set to the total exposure time duration of IP exposure (as defined in [Section 5.1](#)) for that subject.

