## 5. DEFINITIONS

### 5.1 GENERAL

#### **Actual Treatment Received**

The actual treatment received is the investigational product (IP) treatment the subject actually received, regardless of what the subject was randomized to. In cases where a subject received more than 1 IP during a dose, the actual treatment received for that dose will be based on the first IP infusion of the dose the subject received. The actual treatment received for the entire study will be based on the combination of the actual treatment received for the first infusion of the two doses. In cases where a subject received only the 1st dose of IP, the actual treatment received for the entire study will be determined by the actual treatment of the 1st IP dose and the intended treatment of the 2nd

Sponsor: Amgen Inc.

Statistical Analysis Plan

Protocol No: 20130108

10-December-2018/ Version 2.0

---

dose per protocol. The actual treatment for the study will be unplanned if the sequence of the actual treatment of each dose are not described in the protocol.

Specifically, by design for each subject, 2 doses will be administered during the study where each dose consists of 2 infusions, and each infusion consists of 2 boxes. In the cases where a subject receives mismatched boxes (differing IP) among the 2 possible boxes within an infusion, if either box is ABP 798 then the actual treatment for the infusion will be ABP 798.

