### **Duration of IP Exposure**

For subjects who received 2nd dose of IP, the duration of IP exposure will be derived as min (EOS date, analysis data cutoff date) minus date of first IP exposure + 1 day.

For subjects who didn't receive 2nd dose of IP, the duration of IP exposure will be derived as min (EOS date, week 24 [day 175], analysis data cutoff date) minus date of first IP exposure + 1 day.

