### **Subject Incidence Rate**

For adverse event summaries, subject incidence rate for a given event is defined as the number of subjects with at least 1 reported occurrence of the event divided by the number of subjects that received the given treatment or total subjects for the total column. For subjects with multiple occurrences of the same event, the event will only be counted once per subject.

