## **9.8 SAFETY ANALYSES**

All safety analyses will be performed on the Safety analysis set based on subject's actual treatment received. In general, summaries will be provided separately for (1) day 1 to 1st infusion of the 2nd dose of IP (exclusive) for subjects who received 2nd dose or to week 24 (day 175) or EOS (whichever is earlier) for subjects who didn't receive 2nd dose and (2) entire study, unless otherwise specified.

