### **9.8.1 Adverse Events**

All reported AEs will be coded to the appropriate SOC and PT according to the most current version of MedDRA, and the severity of each AE will be graded by the investigator per CTCAE v4.03 criteria.

Only TEAE will be tabulated.

Subject incidence of the following AEs will be tabulated by treatment groups and by SOC, PT, and maximum severity grade per CTCAE v4.03:

- treatment-emergent AEs

Subject incidence of the following AEs will be tabulated by treatment groups and by SOC and PT:

Sponsor: Amgen Inc.

Statistical Analysis Plan

Protocol No: 20130108

10-December-2018/ Version 2.0

- treatment-emergent AEs

Subject incidence of the following AEs will be tabulated by preferred term in descending order of frequency in the ABP798 column:

- treatment-emergent AEs
- grade 3 or higher treatment-emergent AEs
- treatment-emergent AEs leading to discontinuation of IP/study
- treatment-emergent AEs leading to infusion delay/infusion not given
- treatment-emergent AEOIs

For treatment-emergent AEOIs, the point estimate and 95% CI for RD of the subject incidence between ABP and the reference product are provided.

Exposure adjusted subject incidence rate (EAIR) of the following AEs will be tabulated by preferred term in descending order of frequency in the ABP798 column for the entire study:

- treatment-emergent AEs
- treatment-emergent AEOIs

The point estimate and 95% CI for RR of the EAIR between ABP and the reference product are also provided.

AEs leading to discontinuation of IP/study are those with an action taken with Investigational Medicinal Product of “dose discontinued” or those with other action taken of “discontinued from study”. If subjects have an AE for action taken with Investigational Medicinal Product of “dose delayed/not administered” checked, that AE leads to the infusion delay/infusion not given. If an AE leads to multiple actions taken with IP, only the last action will be captured in the eCRF.

Counting of AEs will be by subject, and subjects will be counted only once within each SOC or PT. For tables categorized by severity, subjects with multiple events within a particular SOC or preferred term will be counted under the category of their most severe event with that SOC or preferred term.

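### Entire-study exposure-adjusted AE ratios use conflicting time rules and mix US-arm second courses into the ABP 798 group; the protocol's post-second-dose safety period is also dropped without record

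*SAP*

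**What the plan says.** **Rate and exposure time.** SAP 5.4 divides the number of subjects with an event by the summed time at risk of a first event. For subjects who change product between doses, "the exposure time following each of the doses will be counted in the respective treatment" group. The next rule covers subjects without an event: their time "is set to the total exposure time duration of IP exposure", as defined in SAP 5.1. For anyone given a second dose, SAP 5.1 says "the duration of IP exposure will be derived as min (EOS date, analysis data cutoff date) minus date of first IP exposure", plus one day. That interval covers both doses, and there is no exception for switchers.

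**Grouping.** SAP 5.1 also says "The actual treatment received for the entire study will be based on the combination of the actual treatment received" at each dose, which is a sequence. Protocol 12.6.7 groups the entire study by first dose.

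**Use.** SAP 9.8.1 plans the exposure-adjusted rates only over the whole study: they "will be tabulated by preferred term in descending order of frequency in the ABP798 column for the entire study". It adds: "The point estimate and 95% CI for RR of the EAIR between ABP and the reference product are also provided".

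**Periods.** Protocol 12.6.7 asks for three AE periods, including one from the second dose to week 48/EOS by the three sequences. Protocol 12.6.7.3 asks for an ADA tabulation after the second dose. SAP 9.8 has two periods: "day 1 to 1st infusion of the 2nd dose of IP (exclusive) for subjects who received 2nd dose" (with a day-175 or EOS limit for the others), and the entire study. SAP Appendix 6 follows those two. SAP section 10 lists only changes to analysis sets.

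**The concern.** The two time rules cannot both apply to a US-arm subject who receives ABP 798 as the second dose and has no event. A programmer could split the time at the second dose, book the total in both groups, or book it in one. The answers differ.

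A clean split still leaves a design problem. ABP 798 time consists of first and second courses from the ABP arm plus second courses from the US arm. US time consists of first courses only. Any event whose risk differs between courses then produces a ratio away from 1 for identical products. No first-dose-period version of the rate is planned to set beside it. A reader could take such a ratio, with its 95% CI, as a safety difference in either direction.

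The dropped period matters because it would contain the study's only dedicated summary of AEs and ADA after the switch from US rituximab to ABP 798.

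**Working it through.** The documents state no event rate or rate ratio, so there is no figure to reproduce. The check is the expected ratio when the products are identical.

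**Inputs.** 100 subjects per arm (SAP 3). 85% enter course 2, from the 15% dropout by week 24 (SAP 3.1). Course length W = 24/52 = 0.4615 years. *Assumed:* risk p1 in course 1 and p2 in course 2, constant hazard within a course, and no return to risk in course 2 after a course-1 event.

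**Formulas.** Person-years per subject starting a course with risk p: Y(p) = p·W / (−ln(1−p)). Event-free subjects entering course 2: m = 100·(1−p1)·0.85.
- US, first course only: 100·p1 events, 100·Y(p1) person-years.
- EU, both courses: 100·p1 + m·p2 events, 100·Y(p1) + m·Y(p2) person-years.
- ABP 798, product grouping: the EU expressions plus m·p2 events and m·Y(p2) person-years from the US arm.

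**Equal 10% risk.** m = 76.5. Event-free through both courses: 76.5 × 0.9 = 68.85, worth 68.85 × 0.4615 = 31.78 person-years.
- Clean split: ABP 25.30/110.83, US 10/43.81, EU 17.65/77.32. All are 0.228, so both ratios are 1.00.
- Total booked in both groups: ABP 25.30/(110.83 + 31.78) = 0.177; US 10/(43.81 + 31.78) = 0.132. Ratio 1.34 vs US and 0.177/0.228 = 0.78 vs EU. If subjects whose only event is in course 2 also receive 48 weeks in the US group, US is 10/79.1 = 0.126 and the ratio is 1.40.
- Total booked to US only: ABP 25.30/(110.83 − 31.78) = 0.320, ratio 2.42 vs US. If ABP also keeps the second course, 0.228/0.132 = 1.73.

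Across equal risks of 5% to 20%, booking in both groups gives 1.28 to 1.41 vs US and 0.77 to 0.80 vs EU. Booking to US gives 2.2 to 2.6, or 1.6 to 1.8 if ABP keeps the second course.

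**Clean split, risk differing by course.** For 15% then 5%, m = 72.25: ABP 22.2/107.6 = 0.207, US 15/42.6 = 0.352, EU 18.6/75.1 = 0.248. Expected 95% CIs use SE(log ratio) = √(1/events + 1/events). For 30% then 10% vs US that is √(1/41.9 + 1/30) = 0.239.

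| Risk, course 1 then 2 | vs US (95% CI) | vs EU |
|---|---|---|
| 10% then 5% | 0.69 (0.32–1.49) | 0.89 |
| 15% then 5% | 0.59 (0.30–1.13) | 0.83 |
| 30% then 10% | 0.60 (0.37–0.95) | 0.83 |
| 5% then 10% | 1.64 (0.62–4.36) | 1.12 |

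Grouping by sequence or by first dose, with one time rule for every subject, gives 1.00 in every case.

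**Can other tables replace the dropped period?** Only in part. Infusion reactions are tabulated by infusion. Subtracting the first-period table from the entire-study table finds first occurrences only, because "For subjects with multiple occurrences of the same event, the event will only be counted once per subject".

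By-visit ADA uses fixed study-day windows: Week 24 is days 106–175, Week 30 is 197–245 and Week 48 is 309 onward. Under Protocol Table 1, retreatment on day R moves the samples to R+42 and R+168. R+42 reaches the Week 30 window only if R ≥ 155, and R+168 reaches Week 48 only if R ≥ 141.
- R = 113–140 (week 16 starts the range): samples fall on days 155–182 and 281–308. The Week 24 rule bars visits after the second dose begins, and days 176–196 and 246–308 have no window. Neither sample reaches a visit column.
- R = 141–154: the 6-week sample is lost.

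**The case against.** The specific rule for switchers can be read as overriding the general rule for event-free subjects, which yields the clean split. The larger ratios then come from strained readings that count the same days twice or deny ABP 798 its own second-course time. SAP 5.1 and other sections name sequence groups, and the table shells, which are not among the documents, may settle the columns. Event risks are assumed, and of the four course-varying scenarios only 30% then 10% has a CI vs US that excludes 1; vs EU even that one includes it (0.53–1.30). Before any switch, the first-period tables compare the three products, with risk differences for events of interest. The protocol makes these rates optional and qualifies its period list as general. SAP 5.1 keeps a second-dose ADA baseline, and ADA results outside the visit windows still count in the entire-study incidence.

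Most of this is fair, and it limits the consequence. It does not remove the problem. The SAP text does not state the override. Counting a switcher's time after each dose in separate groups fits product grouping, because that subject belongs to only one sequence. The clean split still compares mixed courses with first courses. The optional status does not excuse an undefined denominator once the SAP has chosen to report the ratio. For the dropped period, no dedicated AE or ADA summary table is listed, and section 10 is silent.

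**Conclusion.** The concern holds. The exposure rule conflicts with itself. On the plain reading, US-arm second courses enter the ABP 798 group, so the entire-study ratios are not randomized comparisons. For identical products, the clean split gives 1.00 only when the hazard is the same in both courses. In the course-varying scenarios it gives 0.59 to 1.64 vs US and 0.83 to 1.12 vs EU. The whole-duration rule moves the ratio even at equal risk. These sizes rest on assumed risks, 100 per arm and 85% retreated; the direction depends on whether risk falls or rises between courses.

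The unrecorded loss of the post-second-dose AE and ADA summaries is a separate departure from the protocol. Both points concern descriptive safety. The PK and DAS28-CRP tests and the first-dose-period risk differences are not affected.

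**What to change.** 1. In SAP 5.4, define event-free time as time within the period and treatment being summarized. State whether a subject with an event in both courses counts in each.
2. Report the exposure-adjusted rates and ratios for the first-dose period (ABP 798, US, EU), ending exposure at the first infusion of the second dose. Treat this as the randomized comparison.
3. For the post-second-dose period and the entire study, report by sequence (ABP/ABP, US/ABP, EU/EU), without moving US-arm second-course time into the ABP 798 group.
4. Restore the protocol's post-second-dose AE and ADA tables. Use the second-dose ADA baseline already in SAP 5.1 and count sample times from the first infusion of the second dose. Otherwise, list and justify the omission in section 10.

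The cost is SAP wording and further runs of existing table programs. No new data are needed.

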### **Subject Incidence Rate**

For adverse event summaries, subject incidence rate for a given event is defined as the number of subjects with at least 1 reported occurrence of the event divided by the number of subjects that received the given treatment or total subjects for the total column. For subjects with multiple occurrences of the same event, the event will only be counted once per subject.

### **Treatment-emergent Adverse Event**

A treatment-emergent AE (TEAE) is defined as an AE that begins or increases in severity or frequency at or after the first study IP administration through EOS. If the AE starts on the same day as the first dose of IP, then the flag indicating whether the AE started prior to the first dose on the adverse event CRF page will be used.

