8.4.3.2 Evaluations at Withdrawal

For any subject who is withdrawn before completing all study visits, the Investigator should:

- Perform all the procedures scheduled for week 48/EOS. The week 48/EOS assessments will be performed no later than 14 days after withdrawal/discontinuation (unless the subject withdraws consent to do so).
- Complete all appropriate electronic case report form (eCRF) screens, providing the date of and explanation for the subject's withdrawal/discontinuation.
- When indicated, arrange for appropriate follow up and/or alternative medical care for the discontinued subject.

If the subject fails to attend a scheduled termination visit, there will be at least 2 attempts to contact the subject via telephone and 2 written communications. If these receive no reply, the subject will be considered lost to follow up.

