11.1.2 Reporting Procedures for Adverse Events

The Investigator is responsible for ensuring that all AEs observed by the Investigator or reported by the subject that occur from the day of randomization until the week 48 visit (or through 28 days after the last dose of investigational product for subjects who discontinue study early) are reported using the applicable eCRF Adverse Event Summary page. AEs observed by the Investigator or reported by the subject that occur after signing of informed consent but before randomization will be recorded.

The Investigator must assign the following AE attributes:

- AE diagnosis or syndrome(s), if known (if not known, signs or symptoms)
- dates of onset and resolution
- severity
- assessment of relatedness to IP
- action taken

AEs must be graded for severity according to the National Cancer Institute (US) Common Terminology Criteria for Adverse Events (CTCAE) version 4.03 (http://ctep.cancer.gov/protocolDevelopment/electronic_applications/ctc.htm).

The Investigator must assess whether the AE is possibly related to the investigational product. This relationship is indicated by a "yes" or "no" response to the question: "Is

there a reasonable possibility that the event may have been caused by the investigational product?"

The Investigator is responsible for reviewing laboratory test results and determining whether an abnormal value in an individual study subject represents a clinically significant change from the subject's baseline values. In general, abnormal laboratory findings without clinical significance (based on the Investigator's judgment) are not to be recorded as AEs. However, laboratory value changes that require treatment or adjustment in current therapy are considered AEs. Where applicable, clinical sequelae (not the laboratory abnormality) are to be recorded as the AE.

The Investigator's clinical judgment is used to determine whether a subject is to be removed from treatment due to an AE. A subject, or subject's legal guardian, can also voluntarily withdraw from treatment due to an AE. If the subject withdraws consent, the subject is encouraged to undergo, at a minimum, an EOS assessment.

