12.6.7.2 Adverse Events

Safety analyses will focus on treatment-emergent AEs. Treatment-emergent events are those that begin or increase in severity or frequency at or after the time of first treatment up to the week 48/EOS visit (or within 28 days following the last dose of study treatment if subject discontinues study early). All treatment-emergent AEs will be summarized by treatment arm and according to the MedDRA system organ class (SOC) and preferred term. Summaries will be provided for the incidence of all treatment-emergent AEs and by severity and relatedness to investigational product. Additional summaries will be presented for SAEs.

All AE data will be listed by subject, and a separate listing will include all SAEs, including any deaths on study.

AEs of special interest ([Section 11.3](#)) will be summarized separately.

The exposure adjusted subject incidence rates of adverse events throughout the study may be tabulated for selected categories of adverse events.

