## 3. STUDY DESIGN

This is a randomized, double-blind, active-controlled 3-arm study in adult subjects with moderate to severe Rheumatoid Arthritis (RA) who have an inadequate response or intolerance to other disease-modifying anti-rheumatic drugs (DMARDs), which must include intolerance or inadequate response to one or more tumor necrosis factor (TNF) inhibitor therapies.

Sponsor: Amgen Inc.

Statistical Analysis Plan

Protocol No: 20130108

10-December-2018/ Version 2.0

---

Approximately 300 subjects (100 per treatment group) will be enrolled. The subjects will be randomized to receive either 2 IV infusions of ABP 798, 1000 mg each, given 2 weeks apart (treatment group A), or 2 IV infusions of rituximab (US) 1000 mg each, given 2 weeks apart (treatment group B) or 2 IV infusions of rituximab (EU), 1000 mg each, given 2 weeks apart (treatment group C) in a double blind fashion. A total of 2 doses will be administered during the study; each dose consists of 2 infusions, 2 weeks apart.

An independent data monitoring committee (DMC) will evaluate the safety data throughout the study, including an initial safety analysis after the first 18 subjects have received the first dose (1000 mg x 2 infusions of either ABP 798 or rituximab (EU) or rituximab (US)).

At week 24, the subjects in treatment groups A and C will continue with and receive the second dose of the same treatment, and the subjects in treatment group B will transition to treatment group A1 and receive ABP 798 1000 mg x 2 as their second dose.

Retreatment may occur earlier, i.e., anytime from week 16 to week 24, in individual subjects, if necessary in the opinion of the Investigator.

The end of study (EOS) will be at week 48 (or 24 weeks after the first infusion of second dose for subjects retreated before week 24), and a final analysis will be performed when all subjects have completed or have had the opportunity to complete the week 48/EOS assessments.

See [Figure 1](#) below for a summary of the study design.

[figure not shown]

Sponsor: Amgen Inc.

Statistical Analysis Plan

Protocol No: 20130108

10-December-2018/ Version 2.0

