### **End of Study Date**

EOS date is the date recorded on the End of Study page of the eCRF for a randomized subject.

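### The SAP ends treatment emergence at the subject's EOS, the protocol at 28 days after the last dose for early leavers, and the change is not declared

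*SAP*

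**What the plan says.** **Protocol.** Section 12.6.7.2 ends treatment emergence at the week 48/EOS visit, "or within 28 days following the last dose of study treatment if subject discontinues study early". Section 11.1.2 collects AEs over a matching period: to the week 48 visit, "or through 28 days after the last dose of investigational product for subjects who discontinue study early". Section 11.2.2 sets the same 28-day limit for SAEs. For a withdrawn subject, section 8.4.3.2 says: "The week 48/EOS assessments will be performed no later than 14 days after withdrawal/discontinuation".

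**SAP.** Section 5.4 defines a TEAE as beginning or worsening "at or after the first study IP administration through EOS", with no 28-day clause. Section 5.1 says: "EOS date is the date recorded on the End of Study page of the eCRF for a randomized subject". Section 9.8.1 says: "Only TEAE will be tabulated". Section 9.8 closes the first safety period, for subjects without a second dose, at the earlier of day 175 and EOS. Section 10 lists changes from the protocol, all of them about analysis sets. The TEAE window is not among them.

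**The concern.** Sites must report an early leaver's events up to 28 days after the last infusion. If that subject's EOS date comes sooner, the SAP stops counting before the protocol does. An event that starts in between is collected but is not a TEAE, so it enters no AE, SAE, fatal-event or AEOI table.

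The planned listings are a weak backstop. In SAP Appendix 6 the listings for discontinuations, fatal outcomes and serious events are all titled treatment-emergent, although SAP 9.8.2 words the SAE and fatal listing without that limit. Protocol 12.6.7.2 promises a listing of all AE data, but Appendix 6 contains none.

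Comparing the safety of ABP 798 with rituximab is a secondary objective. With about 100 subjects per arm, one or two serious events can visibly alter a comparison of rare events.

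**Working it through.** The plan states no figure for this point, so the check compares dates.

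**1. What EOS means in SAP 5.4.** Two readings are possible. SAP section 3 gives a design-level one: "The end of study (EOS) will be at week 48 (or 24 weeks after the first infusion of second dose" for subjects retreated early). SAP 5.1 gives a subject-level date from the eCRF. The SAP's own safety rules settle which is the natural reading. Section 9.8 takes the earlier of day 175 and EOS for subjects without a second dose. Section 5.1 does the same for ADA status, and takes the minimum of EOS date and day 175 for exposure. A week 48 EOS (target day 337 in the SAP visit windows) could never be earlier than day 175, so EOS there must be the subject's own date.

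**2. Gap between the windows.** Gap = (day of last infusion + 28) − EOS day. A positive gap means the SAP window is the shorter one.

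- Last infusion day 15, EOS day 20: (15 + 28) − 20 = 23. Onsets on days 21 to 43 are collected but not tabulated.
- EOS 7 days after any infusion: 28 − 7 = 21 days.
- Last infusion day 15, EOS day 100: 43 − 100 = −57. The SAP counts 57 days more than the protocol read literally.

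**3. How many subjects by week 24.** From the documents: 300 subjects, 15% dropout by week 24, infusions on days 1 and 15, EOS assessments 0 to 14 days after withdrawal. Dropouts: 0.15 × 300 = 45. Assumptions not in the documents: withdrawals fall evenly over days 1 to 168; the last infusion is on day 1 for withdrawal before day 15 and on day 15 otherwise; the EOS date is either the withdrawal day or 14 days later.

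- *EOS on the withdrawal day.* The gap is positive for withdrawal on days 1 to 42: 45 × 42/168 = 11.25 subjects. The shortfalls sum to 301 days (withdrawal days 1 to 14) plus 406 (days 15 to 42) = 707, a mean of 707/42 = 16.8 days. Total: 45 × 707/168 = 189 person-days. The most one subject can lose is 28 days.
- *EOS 14 days later.* The gap is positive for withdrawal on days 1 to 28: 45 × 28/168 = 7.5 subjects. The shortfalls sum to 105 + 105 = 210 days, a mean of 7.5 days. Total: 45 × 210/168 = 56 person-days. The most one subject can lose is 14 days.
- *The other direction.* The SAP window is the longer one for 45 × 125/168 = 33.5 subjects (EOS on withdrawal day) or 45 × 139/168 = 37.2 (EOS 14 days later).

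Against 300 × 168 = 50,400 planned person-days, the shortfall is 56/50,400 = 0.1% to 189/50,400 = 0.4%. Subjects who leave within 28 days of a second-dose infusion would add to this, but no dropout rate after week 24 is given.

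**The case against.** The strongest reply is that the gap is narrow and often empty. It needs a subject who leaves the study, not merely treatment; Protocol 8.4.3.1 lets a subject stop the product and stay in follow-up. It needs an EOS date within 28 days of an infusion, and data that continue past that date. After consent is withdrawn, Protocol 8.4.3.1 uses data only up to withdrawal, apart from public data where permitted, and a subject lost to follow-up yields nothing. How sites date the End of Study page is not in the documents; if it is dated after the 28-day follow-up, nothing is lost. One rule applies to all three blinded arms, the safety analysis is descriptive, and neither SAE reporting nor DMC review depends on the SAP's TEAE flag. All of this stands and limits the size. It does not remove the mismatch or the missing entry in section 10.

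A reader might infer more than the documents support:

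- *That events soon after an infusion are dropped.* Only onsets after EOS and within 28 days of the last infusion are lost. Infusion reactions are searched on the infusion day and the next day (SAP Appendix 5), so those starting by EOS stay in. So does an event that starts before EOS and later proves fatal.
- *That every safety table is affected.* Laboratory, vital-sign and ADA tables do not use the TEAE flag.
- *That about 45 subjects are affected.* That is the whole dropout allowance to week 24.
- *That early leavers are the subjects most likely to have serious events.* Nothing in either document shows this.

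**Conclusion.** The two documents define different windows for early discontinuers, in both directions, and the SAP does not say so. The SAP is shorter when the EOS date is less than 28 days after the last infusion, and longer when it is more than 28 days after. The shorter case matters more, because events the protocol requires sites to collect then appear in no AE table.

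The effect is probably small: about 7.5 to 11 of 300 subjects and 56 to 189 person-days by week 24. That range rests on evenly spread withdrawals and on an EOS date 0 to 14 days after withdrawal. It is an upper figure for that period to the extent that consent withdrawal or loss to follow-up ends data collection. The conclusion also rests on reading EOS in SAP 5.4 as the subject's own date. The change should be made because it is cheap and the comparison concerns rare events, not because a large bias is shown.

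**What to change.** 1. **SAP 5.4:** define a TEAE as starting or worsening from the first infusion through the later of the subject's EOS date and 28 days after the last infusion. This restores the protocol's 28 days and keeps the longer SAP window for those who leave later.
2. **SAP 9.8:** align the first-period cut for subjects without a second dose. If it stays at the earlier of day 175 and EOS, the restored events would still drop out of the first-period tables.
3. **SAP 5.1 (duration of exposure) and 5.4 (EAIR):** extend exposure time only through the date the subject was actually followed for AEs, capped at the same end date. Giving every subject 28 days would credit unobserved time at risk and pull the EAIR down.
4. **SAP section 10:** list the change and say that it differs from the protocol's literal window for later leavers.

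The cost is a few aligned sentences and the matching programming of the TEAE flag, period cut and exposure end date. No new data are needed: Protocol 11.1.2 and 11.2.2 already require collection over the added days.
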